2.2 BACKGROUND

Excessive opioid use is a national emergency. There were >350,000 emergency department visits in 2015 due to opioid poisoning.¹ There were 47,600 opioid overdose deaths in 2017,² and the death rate is growing fastest in rural areas (325% since 1999).³ There are an estimated 2.1 million Americans meeting diagnostic criteria for an OUD, including 1.7 million with a prescription pain reliever use disorder and 0.7 million with a heroin use disorder.⁴ Medication Assisted Treatment (MAT) with either buprenorphine, methadone, or naltrexone represents the gold-standard intervention for OUD⁵ and significantly reduces risk for overdose or death.⁶ However, only 20% of Americans with OUD received any formal or informal addiction treatment in the past year.⁷ Moreover, even in addiction treatment settings in the US, only 32% of patients with OUD were prescribed MOUD in 2016.⁸ Lack of *access* and *engagement* in MOUD is clearly a driver of poor OUD outcomes, especially in rural areas lacking addiction services.

To close this *engagement* gap, more patients with OUD need *access* to MOUD in primary care settings.^{9,10} We conceptualize *access* to care as the potential ease of having encounters with a broad array of healthcare providers (Figure 1).¹¹ Integrating OUD treatment into primary care improves geographical (i.e., travel), temporal (e.g., wait time), and cultural (e.g., stigma) access. Our conceptualization of *engagement* is participating sufficiently in a treatment plan to potentially experience a therapeutic effect. Treatment engagement depends on patient perceptions

about access to care, and the perceived need for and expectations from treatment.¹¹ With adequate access and engagement, individuals have the opportunity to receive high *quality* care and improved

[figure not shown]
outcomes. However, MOUD delivered in primary care can only improve outcomes if the quality of care is high.

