Here the outcome measured at time t , for subject i , in clinic c is denoted by Y_{cit} . To account for the cluster-randomization this model includes a random effect for each clinic denoted as u_c . In order to allow a general longitudinal correlation and variance structure we use three subject-specific error terms denoted by u_{cit} for $t=0, 3, 6$ months. We assume a general 3×3 covariance model for these error terms to provide maximal validity to inference regarding change over time. To allow for potential non-linear change over time, we will enter time as a nominal variable by including dummy codes for the 3 and 6 month time points represented by the variables (3 months) and (6 months). Intervention main effects and interaction between intervention and time indicators capture the difference between intervention clinics and control clinics at each wave – with β_1 representing the adjusted mean difference across intervention groups at baseline (adjusting for the design variables) -- with $\beta_1 + \beta_4$ representing the adjusted mean difference across intervention groups at 3 months – and with $\beta_1 + \beta_5$ representing the adjusted mean difference across intervention groups at 6 months. Therefore, the primary contrasts are given by with β_4 as the 3-month intervention effect, and β_5 as the 6-month intervention effect. Note that each intervention effect accounts for the potential imbalance of outcomes across the intervention and control groups at baseline due to the small number of clusters (β_1) and this is removed from the cross-sectional mean contrasts at each follow-up time to define the key intervention effect parameters. *DesignVars* denotes a vector of covariates that includes: 1) low vs high fidelity, which must be controlled because it was a design/stratification variable for some clinics, and 2) additional covariates theoretically related to both the primary outcome and the probability of not completing follow-up surveys which will aid in enhancing validity against missing data and improving precision of estimation. Specifically, we will include: 1) worried about not have stable housing in the next two months, 2) being on parole or probation and/or presently awaiting charges, trial or sentencing, 3) opioid craving, 4) pain, 5) Audit-C, 6) provider trust (APAC item #6), and 7) any use of other drugs (dummy coding for each class of drug). The pre-specified primary effect of interest will be β_5 , which represents the difference in change from baseline between intervention and control clinics at 6 months. Table S2 presents a shell table for the primary outcome and Figure 2 presents a shell plot. Table S3 presents a shell table for the secondary outcomes.

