4.2 Moderated Mediation Analyses (Hypothesis 2)

Hypothesis 2: MOUD consistency will fully mediate any improvements in patient-reported outcomes observed in intervention clinics compared to control clinics.

These analyses will compare the different pathways through which the intervention transmits effects. We hypothesize that the intervention should lead to greater use of MOUD (A path in Figure 2) because of the care managers' encouragement of MOUD initiation and adherence, leading to improved outcomes. We also expect the intervention will cause MOUD use to be more effective (Moderation path in Figure 3) in improving outcomes because of the use of the OTRI measurement-based care instrument and dosage recommendations by the consulting psychiatrist. Because the proposed moderation violates the assumption of mediation, we will first test the moderation (Figure 3), followed by a mediation or moderated mediation analysis (Figure 2).^{13,14} This analysis will be performed in three stages. In the first stage, we will use the same model as described in equation 1 to assess the MOUD consistency x intervention (moderator) interaction (Figure 3) (Table S4a). In the second stage, we will test the effect of the intervention on the mediator (A path in Figure 2) (Table S4b). In the third stage, the mediator will be included (B path), controlling for the direct effects of treatment (C path in Figure 2) (Table S4b). If the moderation is statistically significant, the MOUD consistency x intervention interaction will be included in this model. Models will be run separately for 3- and 6-months.

Figure 2. Path diagram for mediation model

[figure not shown]
[figure not shown]

Figure 3. Path diagram for moderation model

For the moderation analysis, we use the same model structure and design variables as the primary outcome. We will include MOUD consistency and intervention as main effects and the MOUD Consistency x intervention interaction. (Table S4a).

To calculate A path, the main effect of treatment on the mediator, we will use the same model as the primary outcome (Table S4b). Direct effects on MOUD consistency (path A) will be presented as an adjusted mean. To account for the potential imbalance of the mediator across the intervention and control groups at baseline due to the small number of clusters, the main effect for intervention at baseline is included.

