To calculate the B and C paths, we will include the mediator and intervention-mediator interaction in predicting outcomes (Table S4b). To calculate the total effect of the mediator for the intervention, we will sum the main effects and interactions. To calculate indirect effects (Table S4b), we will multiply the A path by the B path for the mediator. Because the distribution of the product may be non-normal, we will calculate 95% confidence intervals using bootstrapping.

5. Missing data

Estimates from multilevel models are unbiased under conditions of *Missing at Random* (MAR), which means that the mechanism that causes missingness is included in the model. Most relevant to the current analysis, in longitudinal data, estimates will be unbiased when

missingness is caused by previously observed values of the dependent variable, but not if missingness is caused by the unobserved value at the missing wave. We will attempt to make the MAR assumption more plausible by incorporating reasons for missingness into the model. We will analyze data with maximum likelihood estimation (MAR assumption) and no auxiliary information.¹⁵

6. Power Calculation

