	Overall n (%) or μ (SD)	Intervention Group n (%) or μ (SD)	Control Group n (%) or μ (SD)
Age (years)			
Are you of Hispanic, Latino/a/e or Spanish origin?			
Yes			
No			
Missing			
Race			
American Indian, Alaska Native, or other Indigenous group			
Native Hawaiian or other Pacific Islander			
African American or Black			
White			
Multi-race			
Another Identity			
Missing			
Current Gender Identity			
Man			
Woman			
Non-binary or gender fluid			
Missing			
Marital Status			
Divorced			
Married or living with a partner			
Separated			
Single, never married			

Missing

Housing Status

No, not living in stable housing

Yes, living in stable housing

Missing

Concern about Future Housing

No, not worried about housing in the near future

Yes, worried about housing in the near future

Missing

Parole/Probation

No

Yes

Missing

Awaiting charges, trial, or sentencing

No

Yes

Missing

Currently mandated by a court to receive addiction treatment

No

Yes

Missing

Individual Readiness to Change (ICR; range: 0-10)

Importance for change

Confidence for change

Readiness for change

Clinical Characteristics:

Veterans Short Form 12 Mental Health Component Summary score

(MCS; range: 0-100)

Opioid Use:

Any opioid use in the past 30 days

Number of days of opioid use in the past 30 days

Opioid Craving:

Not at all

Slightly

Moderately

Considerably

Extremely

Medication for OUD:

Lifetime

Current

Alcohol Use: (AUDIT-C; range: 0-12)

Other Drug Use: Any use in the past 30 days

Cocaine and/or crack use

Other stimulant use

Sedative and/or tranquilizer use

Cannabis use

Inhalant use

Other illegal drug use

Recent Overdose Experience

Ever overdosed

Number of previous overdoses

Overdosed in the past 6 months

Number of overdoses in the past 6 months

Pain Level (PEG; range: 0-10)

Hopkins Symptoms Checklist (SCL-20; range: 0-4)

Anxiety (PROMIS Measure - Anxiety 8a - Adult v1.0: range: 36.4-76.8)

PTSD Checklist (PCL-5; range: 0-80)

Table S2. Multiple primary outcomes across intervention conditions

	Intervention		Control		Treatment Effects		
	Mean (SD)	95% CI	Mean (SD)	95% CI	Adjusted Odds Ratio	95% CI	Cohen's d
Opioid Use							
Baseline							
3 months							
6 months (primary outcome)							
					Adjusted Mean Difference	95% CI	Cohen's d
MCS							
Baseline							
3 months							
6 months (primary outcome)							

Table S3. Treatment effects for secondary and exploratory outcomes at 3 and 6 month follow-up

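### The MOUD-to-outcome path and the arm-specific MOUD slopes are non-randomised comparisons, yet they reuse the primary model's covariates and omit the collected baseline readiness-to-change scores

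*SAP*

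**What the plan says.** Full mediation by MOUD is hypothesis b of the primary objective (protocol sections 3 and 9.1) and Hypothesis 2 of the SAP. SAP section 3 measures MOUD consistency from patients' own reports of use in the past 30 days.

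SAP 4.2 sets out three stages:

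- **Moderation:** "we will use the same model as described in equation 1 to assess the MOUD consistency x intervention (moderator) interaction". On covariates: "For the moderation analysis, we use the same model structure and design variables as the primary outcome".
- **Path A:** the effect of the intervention on MOUD consistency, with the primary outcome's model.
- **Paths B and C:** "In the third stage, the mediator will be included (B path), controlling for the direct effects of treatment". A later paragraph says: "To calculate the B and C paths, we will include the mediator and intervention-mediator interaction in predicting outcomes". Neither sentence names a covariate set.

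For the indirect effect, "we will multiply the A path by the B path for the mediator", with a bootstrap 95% interval.

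SAP 4.1 defines the design variables as CoCM fidelity (a stratification variable) and "additional covariates theoretically related to both the primary outcome and the probability of not completing follow-up surveys". The stated purpose is validity against missing data and better precision. The seven items are housing worry, legal status, opioid craving, pain, AUDIT-C, provider trust and other drug use.

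Shell Table S1 has a row that begins "Individual Readiness to Change (ICR; range: 0-10", with importance, confidence and readiness beneath it. Protocol 8.1 schedules this instrument at baseline. It appears in no outcome, moderation or mediation model.

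**The concern.** Randomising clinics protects path A. It does not protect a comparison between patients who take MOUD consistently and patients who do not. That comparison is free of confounding only if the model contains the common causes of MOUD use and outcome. The SAP's covariates were selected on another rule: relation to outcome and to survey non-completion. Relation to MOUD use is not part of it.

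Protocol 2.2 says that treatment engagement depends on patient perceptions "about access to care, and the perceived need for and expectations from treatment". Readiness to change is a plausible measure of that motivation. A patient who is readier to change may both keep taking MOUD and do better for other reasons. If so, path B is above zero even when MOUD does nothing, and because the indirect effect is A times B, the error passes into the mediated effect. The slopes in Table S4a share the problem.

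The SAP reorders its stages because moderation would violate an assumption of mediation. It does not state the assumption of no confounding between mediator and outcome, and it plans no sensitivity analysis for it.

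**Working it through.** The plan gives no figure for path B, so there is none to reproduce. The size is shown by illustration for a continuous outcome such as MCS.

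**Inputs**

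- Analysed patients: 254 enrolled (SAP 6) with 20% attrition (protocol 9.2): 254 x 0.80 = 203.
- True B = 0, so every significant indirect effect is false.
- Assumed: path A = 0.5 SD; baseline to 6-month outcome correlation 0.5; readiness correlated r with MOUD consistency, baseline outcome and follow-up outcome. The documents give none of these, so r is varied.
- Clustering is ignored and baseline outcome enters as a covariate, as an approximation to the joint model in Equation 1.

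**Path B, with baseline outcome in the model.** Within arm, MOUD consistency correlates r x r = r² with each outcome. Its coefficient given baseline outcome is therefore

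b = (r² - 0.5r²) / (1 - r⁴) = 0.5r² / (1 - r⁴).

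Its standard error is about √[0.75 / (203(1 - r⁴))] ≈ 0.061. Path A has standard error 2/√203 = 0.140, so z = 0.5/0.140 = 3.56 and the chance that A is significant is P(Z > 1.96 - 3.56) = 0.945. Requiring both paths to be significant approximates the product interval:

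| r | b (SD) | b/SE | P(B significant) | x 0.945 | Simulated indirect effect |
|---|---|---|---|---|---|
| 0.1 | 0.005 | 0.08 | 5.1% | 4.8% | about 5% |
| 0.2 | 0.020 | 0.33 | 6.3% | 5.9% | 6% |
| 0.3 | 0.045 | 0.74 | 11.6% | 10.9% | 11% |
| 0.4 | 0.082 | 1.34 | 26.8% | 25% | 23% |

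With readiness added, b returns to 0. The expected rate is 5% x 0.945 = 4.7%, and about 5% was simulated.

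**Baseline outcome left out.** Then b = r². The simulated rates at r = 0.2, 0.3 and 0.4 are 9%, 24% and 58%. The baseline outcome therefore removes more than half of the rate at 0.3 and 0.4.

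**Baseline outcome unrelated to readiness.** A separate run (203 patients, 4,000 repetitions, readiness score of assumed reliability 0.8) set readiness independent of baseline outcome, so baseline adjustment could not help. With the readiness-MOUD correlation and the readiness-outcome coefficient both at 0.1, 0.2, 0.3 and 0.5, false positives for path B were 5.8%, 10.6%, 30% and 99%. Adding the score brought them to 5.3%, 5.7%, 6% and 20%.

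**Moderation.** In the same run, the bias in an arm's slope is about (readiness-MOUD correlation in that arm) x (readiness-outcome coefficient).

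- Equal selection, 0.3 in both arms, coefficient 0.3: each slope is biased by 0.3 x 0.3 = 0.09 SD, but the difference is 0. Simulated false positives for the interaction across the equal-selection settings: 4-6%.
- Unequal selection, 0.1 in one arm and 0.4 in the other: 0.3 x 0.1 = 0.03 against 0.3 x 0.4 = 0.12, a difference of 0.09 SD. Its sign depends on which arm has the stronger link. Simulated false positives: 11-12%, falling to 6% with readiness and its interaction with arm in the model.

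**The case against.** The strongest reply is that the SAP's covariates already do much of this work. They must relate to the primary outcome as well as to non-completion. Craving, provider trust (an item of the access instrument, and access is part of the protocol's engagement model), legal status and other drug use are plausible common causes of MOUD use and outcome. The Equation 1 structure also carries the baseline outcome. This stands: r above has to be read as what remains after those items, and at 0.1-0.2 the harm is negligible.

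Three further points stand in part:

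- **Timing.** Table S1 records current and lifetime MOUD at baseline. Patients at intervention clinics may have had up to 14 days of the intervention before enrolment (protocol 5.2), and the baseline survey runs over days 1-14 (protocol 1.3). Baseline ICR may partly reflect treatment already begun. It still precedes MOUD use and outcome as measured at 3 and 6 months.
- **Construct.** The documents never link ICR to perceived need or expectations. That link is an inference, though a natural one.
- **Model strain.** The SAP's modification table records that a covariate was dropped to help convergence. Three related scores add to that strain.

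A reader might also infer that the moderation test must be distorted because control patients on MOUD select themselves. The documents do not say so. Control providers may prescribe MOUD (protocol 6.1.1), and control patients are referred to specialty care for OUD. Selection that differs by arm is plausible, because only the intervention promotes MOUD, but neither its size nor its direction is given.

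**Conclusion.** The concern holds as a gap in adjustment, not as a demonstrated bias. Path B and the slopes in Table S4a are non-randomised, their covariates were not chosen with MOUD use in mind, and a relevant baseline measure is collected and left out. More motivated patients' better outcomes can therefore be credited to MOUD.

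Under the stated assumptions (true B = 0, about 203 patients, path A of 0.5 SD, baseline outcome in the model), the false-positive rate of the indirect effect is about 5-6% at r = 0.1-0.2, 11% at 0.3 and 23% at 0.4. Adding readiness returns it to about 5%, or somewhat above if ICR measures readiness with error. A smaller path A would lower the rates; a baseline outcome that carries little information on readiness would raise them.

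Three stronger readings are not supported. The covariates were not chosen for survey non-response alone. The documents do not show that the indirect effect will be spurious, since they give no association between readiness and MOUD use or outcome. The MOUD-by-intervention contrast is biased only if selection into MOUD differs by arm, and then in either direction. Path A and the randomised primary comparison are untouched.

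**What to change.** In SAP 4.2, state the covariate set for the B/C-path and moderation models: the primary design variables plus the three baseline ICR scores (importance, confidence, readiness), or their mean if the model does not converge. Specify the baseline scores, because protocol 1.3 also schedules the instrument at 3 and 6 months while 8.1 has it at baseline only. State that path B and the MOUD slopes in Tables S4a and S4b will be reported as observational associations.

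The cost is SAP wording and covariates already collected: a few degrees of freedom, some missing ICR items whose handling must be stated (protocol 9.4.2 allows multiple imputation for skipped items), and possible convergence strain, for which the mean score is the fallback. Confounders other than readiness remain, which is why the observational label is needed as well.

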PTSD – Posttraumatic Stress Disorder

SCL-20 - Hopkins Symptom Checklist

WFS – Written For Study

Mediator variables

The hypothesized mechanism of action is engagement in MOUD, which we define as initiation and “consistent” refilling of the MOUD medication, which has been demonstrated to be correlated with good outcomes.¹² MOUD consistency is defined as the ratio of the number of days they reported taking the MOUD medication (numerator) to the number of days during the reporting period for which it was prescribed (denominator).¹² This is measured from self-reported MOUD use in the past 30 days which is assessed using survey questions written for the study.

4. Analyses

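### If the MOUD × intervention interaction enters the mediation model with MOUD consistency uncentred, the C path leaves out part of the direct effect, so a C path near zero would not establish full mediation

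*SAP*

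**What the plan says.** SAP section 4.2 sets the hypothesis: "MOUD consistency will fully mediate any improvements in patient-reported outcomes observed in intervention clinics compared to control clinics". The same section also predicts an interaction: "We also expect the intervention will cause MOUD use to be more effective".

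The outcome model includes the mediator while "controlling for the direct effects of treatment (C path in Figure 2"). The section gives two rules on whether the interaction belongs in that model. The staged description is conditional: "If the moderation is statistically significant, the MOUD consistency x intervention interaction will be included in this model". The later description of the path calculations is not: "To calculate the B and C paths, we will include the mediator and intervention-mediator interaction in predicting outcomes (Table S4b").

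Main effect and interaction are combined for the mediator only: "To calculate the total effect of the mediator for the intervention, we will sum the main effects and interactions". For the indirect effect, "we will multiply the A path by the B path for the mediator"; which B is meant when the interaction is present is not said. The mediator is a proportion: "MOUD consistency is defined as the ratio of the number of days they reported taking the MOUD medication (numerator) to the number of days" prescribed in the reporting period, so zero is the bottom of its scale.

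No centring is stated, nor any MOUD level for the direct effect. Shell Table S4b has rows for path A, path B and the indirect effects, but none for the C path or the total effect.

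**The concern.** Complete mediation by MOUD is Hypothesis b of the primary objective in Protocol section 9.1. Judging it requires a direct effect that means what is left once MOUD is held at the level patients would have had without the intervention. When arm and mediator interact, the bare intervention coefficient is not that quantity.

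The part left out is what the SAP's own moderation hypothesis predicts: the same MOUD use giving a better outcome in intervention clinics. That gain does not pass through more MOUD use, so it counts against full mediation. It matters only if control patients take some MOUD. Protocol section 6.1.1 lets control-arm providers prescribe it, and SAP Table S1 tabulates current MOUD at baseline.

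**Working it through.** The documents give no value for path A, path B, the interaction or control-arm MOUD, so there is no planned figure to reproduce. All slopes and MOUD levels below are assumptions.

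**1. Algebra for MCS (linear model), analysed wave only.** Let T be arm (0/1), M MOUD consistency, m0 and m1 its control and intervention means, and A = m1 − m0. The outcome model is Y = k + c·T + b·M + θ·T·M.

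- Control mean: k + b·m0. Intervention mean: k + c + (b + θ)·m1.
- Total effect: **A(b + θ) + [c + θ·m0]**.
- The C-path coefficient is c, the effect at M = 0. A(b + θ) plus c misses θ·m0.
- If B is read as b alone, total = A·b + [c + θ·m1], and the missing term is the larger θ·m1.

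**2. Algebra if the baseline rows of Eq. 1 are kept.** Assume one θ for all waves and let Δm0 be the control-arm change in MOUD. The difference in change is A(b + θ) + [β5 + θ·Δm0], with A now the between-arm difference in MOUD change. The C path is then β5, and the missing term is θ·Δm0. Subtracting one constant from M alters β1 but leaves β5 unchanged, so centring alone does not repair this version.

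**3. Direct share when the C path is exactly zero.** Share = θ·m0 / [θ·m0 + A(b + θ)].

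| Assumed inputs | Missing term | A(b + θ) | Direct share |
|---|---|---|---|
| m0 0.4, A 0.2, b = θ = 0.575 SD (total 0.46 SD) | 0.23 | 0.23 | 50% |
| m0 0.45, A 0.18, b = θ = 4 MCS points | 1.80 | 1.44 | 56% |
| same, θ = 2 | 0.90 | 1.08 | 45% |
| same, θ = 8 | 3.60 | 2.16 | 62.5% |
| b = θ = 4, A 0.18, baseline rows kept, Δm0 0.05 | 0.20 | 1.44 | 12% |
| same, Δm0 0.10 | 0.40 | 1.44 | 22% |
| same, Δm0 0.20 | 0.80 | 1.44 | 36% |

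Over a grid of m0 from 0 to 0.6, A from 0.1 to 0.4 and θ/b from 0.25 to 2 (analysed wave only), the share runs from 0% to 80%, median 31%. It is 0% when m0 = 0 and 5% to 80% when m0 is at least 0.1. The maximum is m0 0.6, A 0.1, θ/b 2: 1.2 / (1.2 + 0.3) = 80%.

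**4. How often the pattern could arise.** The pattern is a significant interaction with a non-significant C path. Simulations used 3,000 runs, no clustering and c = 0.

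- First row of the table (n = 254, binary M): the interaction was significant in 60% of runs, C was non-significant in 95%, and both occurred together in 58%. The direct effect at control-arm MOUD was significant in 43%.
- MCS-scale rows (n = 203, which is 254 less 20% loss; residual SD 13.5 = 6.22/0.46): the pattern occurred in about 5%, 13% and 42% of runs for θ = 2, 4 and 8. At θ = 4 with the interaction always fitted, C averaged about 0 (SD 3.1), while the direct effect at the control mean averaged about 1.8 (SD 2.0). With the interaction left out, C averaged about 2.2.

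**The case against.** Several stronger readings are tempting, and the documents do not support them.

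- *The plan will declare full mediation when C is near zero.* The SAP states no criterion for full mediation and gives C no row in Table S4b. The wrong conclusion is a risk left open, not a written rule.
- *The interaction is always in the model.* The staged description adds it only after a significant test. Without it, C is not the effect at zero MOUD and, in the simulation, did not hide the direct effect. With modest slopes the test would often be non-significant.
- *About half of the effect would be hidden.* That follows from particular assumed inputs. The share can be zero, and with baseline rows kept it was 12% to 36% in the cases shown.
- *MOUD consistency is uncentred and θ is added to B in the indirect effect.* The SAP is silent on both.
- *The same sums hold for both outcomes.* Opioid days use a logit link (SAP section 4.1), where sums and products of coefficients do not decompose the effect this way.

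It is also fair that the SAP recognises moderation as a breach of a mediation assumption and so tests it first. The effect at zero MOUD is itself a legitimate controlled direct effect, and trial success rests on the two primary outcomes, which this leaves untouched.

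What stands is the algebra. Reordering the tests and adding the interaction does not redefine the direct effect. Under either rule, the interaction enters when the moderation test is significant, and an uncentred C then does not add up with A × B to the total.

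**Conclusion.** The point holds for MCS whenever the interaction is in the model and MOUD consistency is left uncentred. The C path is then the intervention effect at zero MOUD (or, with baseline rows kept, the effect had control-arm MOUD not changed). A value near zero would not establish Hypothesis 2. The missing term is θ × control-arm mean MOUD, or θ × the control-arm change.

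Its size cannot be derived from the documents: 0% of the total effect if control-arm MOUD is zero, up to 80% on the assumed grid, always taking C as exactly zero. The chance of meeting the pattern depends just as strongly on assumed slopes, from about 5% to 58% in the cases run. This is a correction worth making to the mediation analysis. It does not bear on the primary comparisons.

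**What to change.** In SAP section 4.2:

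1. Reconcile the two statements on when the interaction enters the outcome model, and say whether baseline rows are kept.
2. With the interaction in, define the direct effect for MCS as c + θ × control-arm mean MOUD at the analysed wave (equivalently, centre MOUD there) and the indirect effect as A(b + θ). If baseline rows are kept, use β5 + θ × control-arm change instead.
3. For opioid days, obtain the same direct, indirect and total effects by standardising model predictions.
4. Bootstrap the direct and indirect effects together.
5. Add direct-effect and total-effect rows to Table S4b.
6. State that full mediation is judged on this direct effect, not on the uncentred C coefficient.

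The cost is SAP wording and slightly more analysis, mainly the standardisation for opioid days, with no new data. Full mediation becomes harder to claim.
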